#### 4.1 Inclusion Criteria

- Adults 65 years or older.
- Chronic disease (musculoskeletal, neurologic, internistic)
- Increased risk of falling (Berg Balance Scale (BBS) score 49 or less).
- Self-reported history of imbalance (*Anamnestisch: Unsicherheit beim Gehen oder Stehen*)
- Living in the community (at own home) or retirement or nursing home.
- Ability to participate in 1-hour group-based sessions (medical assessment).
- Able to leave home on their own at least twice per week (e.g. for doctors visit, shopping)
- Patient's written informed consent has been obtained

#### 4.2 Exclusion Criteria

- Medical conditions limiting participation (e.g. terminal illness, heart failure NYHA III-IV, unstable angina pectoris, uncontrolled seizure disorder, decompensated lung disease with less than ordinary activity leading to dyspnoea, cancer in advanced stage, chemo- or radiotherapy ongoing or during last three months, amputation of one or both legs).
- Complete dependence on rollator (wheeled walker).
- Visual, hearing or language problems affecting understanding of trial documents and procedures.
- Major cognitive impairment (MoCA score 18 or less).
- High risk for individual support during group session.
- Urge incontinence affecting group sessions.
- Severe personality disorder, psychiatric disease, alcohol use disorder or other substance use disorders affecting participation of group classes and regular practicing.
- Life expectancy of less than 1 year.
- Permanent confinement to bed to be expected in less than a year.
- Participating in regular Tai Chi or EYT exercises within last 6 months.
- Participating in vigorous sports for exercise within last month (e.g. training in fitness club or other sport activity inducing sweating and breathlessness or skiing and mountaineering in high mountains).
- Patient without legal capacity who is unable to understand the nature, significance and consequences of the study.

- Participation in a clinical trial within the 3 months before the start of this study (screening) or simultaneous participation in another study which could interfere with this study.

## 5 Recruitment and Enrolment of Subjects in the Study, Randomisation

### 5.1 Patient recruitment

A recruitment strategy will be set up to enrol the patients, but particularly to also invite economically disadvantaged patients, patients living a reclusive and less active life: The recruitment strategy includes:

- announcement through local media (magazine articles; radio interviews, display)
- announcement through a website: <https://www.uniklinik-freiburg.de/entaier-studie.html>
- flyers and posters
- oral presentations in nursing/retirement homes, meetings of senior citizens;
- personal contact (in person or via telephone) of the following persons and institutions, to inform them about the trial, provide trial brochures and flyers so they can inform patients about the trial:
  - local resident primary care physicians, orthopaedic doctors, neurologists, internists, dentists,
  - geriatric wards and ambulances, outpatient and inpatient trauma surgeries (to address patients after falls),
  - local nursing and retirement homes,
  - outpatient nursing services, household help,
  - other organisations providing help at home or working in the community (e.g. neighbourhood assistance, “meals on wheels”, social workers, priests),
  - social welfare office,
  - Senior Citizens' Office (*Seniorenbüro*), Senior Council (*Seniorenrat*),
  - organisations representing elder people (e.g. *Caritasverband*, *Diakonie*, *BAGSO*, *Paritätischer Wohlfahrtsverband*, *Landesseniorenvertretung*, *Kuratorium Deutsche Altenhilfe*, *Gesundheit aktiv*),
  - health insurances and their local representatives, therapists, Tai Chi and EYT organizations.

These will inform patients about the trial (oral and handing out flyers and address of website) and encourage them to get into contact with the local study sites.

### 5.2 Patient enrolment

Patients being informed about the trial and being interested will contact the local study sites or study teams.

#### Pre-screening

A pre-screening will then be done by telephone or in person. Information about the trial is given; inclusion and exclusion criteria as well as issues of compliance (regarding randomised

treatment allocation, documentation, EYT or Tai Chi group sessions, training at home, visits, follow-up) are discussed.

### **Waiting time**

Patients that appear to be eligible for the trial and are interested in participation will enter a waiting time, until 15 or 30 patients could be enrolled.

### **Final Screening, Baseline, Enrolment**

After the waiting time, patients that appear to be eligible, are still interested and have free time to join the EYT and Tai Chi group session, are invited for detailed information, final screening (see section 4) and baseline assessment (see section 6.3).

Final screening will be done by the investigator in person. Patients will receive detailed information about the trial. The patient will be asked for his/her written consent. It is imperative that written consent is obtained prior to any trial-specific procedures, including BBS, MoCA, which are needed to check the eligibility. Patients are asked to provide a list of all medications from their primary care doctor and may also be asked to provide medical reports (e.g. from last hospital stay or consultant) to check eligibility. Patients fulfilling inclusion criteria and giving informed consent will then have baseline assessment (see section 6.3).

The investigator will then record the details of these trial patients on the following trial-specific lists:

- Subject Screening log: for the documentation of the trial patients who were checked for eligibility. The following will be entered: the identification code\*, the dates of written consent, and screening, as well as details of whether the patient was enrolled in the trial and, if not, the reason for not enrolling the patient.
- Subject identification log: A confidential log of the names of all trial patients with the identification code\* assigned to each patient at the time of enrolment in the clinical trial. With this list, the identity of each patient can be revealed. The list must be kept confidential and must not leave the institution. It must remain at the study site and must not be copied or otherwise passed on! CRAs, auditors and representatives of authorities must be allowed to inspect the list on request.

\* Patient identification code: A unique trial-specific identification number will be assigned to the patients. The first 2 digits correspond to the number of the study site, the next 3 digits stand for the consecutively screened patients at the particular study site, for example: 01001 (study site 1, patient 1), so that each patient is numbered uniquely across the entire database.

### **Start of treatment and observation period**

After baseline assessment, patients are randomly allocated to the three groups. EYT and Tai Chi sessions (see section 8) have to start within 4 weeks after baseline assessment. The study books have to be handed over to the patients before the first EYT and Tai Chi session starts,

preferably at the same place and the same day but not more than 7 days before. The content of the study books has to be explained, as well as the visits, the fall prevention brochure and particularly also the documentation of falls. The group receiving standard care alone will be invited to the study site and receive the study book and concerning explanations at a comparable time (not more than 10 days apart). Patients will be recommended to visit their primary care physician to discuss fall prevention measures. Observation period and documentation starts with handing out this study book.

The study book contains: general instructions regarding the study book, contact information, a calendar, the fall diary and instructions how to use it, the brochure on fall prevention, a page for writing down their personal goals, pre-franked envelopes to send back the fall diary every month. The study book for patients allocated to the EYT and Tai Chi groups also contains: training diary and instructions how to use it, treatment manuals and instructions on how to practice regularly and safely, a DVD and an internet-link for a video for practicing.

### **5.3 Randomisation – general and methodological considerations**

After baseline assessment (see sections 5.2 and 6.3) batches of ideally 15 patients should be randomised to the 3 research arms: EYT or Tai Chi or standard care alone (control). In exceptional cases – e.g. when recruitment is much slower or faster than expected - 12 or 18 patients can be randomised at once, respectively.

If possible, two batches of 15 (or 12 or 18) patients should be enrolled and randomised to 2 x 3 groups. If two batches with 15 (12, 18) patients are randomised concurrently (or within a few days), it is recommended to subdivide the batches depending on their risk of falling (BBS), to randomise one batch of 15 (12, 18) patients with lower BBS and one batch of 15 (12, 18) patients with higher BBS.

The randomisation code will be generated by the CTU using the following procedure to ensure that treatment assignment is unbiased and concealed from patients and investigator staff. For each batch size (12, 15 and 18) a separate randomisation fax form and randomisation lists will be prepared. Randomisation will be stratified by clinical site and performed in blocks of length 12, 15 or 18 in a ratio of 1:1:1. The randomization code will be produced by validated programs based on the Statistical Analysis System (SAS).

#### **Central randomisation by fax**

The patient identification codes of the batch of patients assigned for the trial (see section 5.3) will be entered on the randomisation fax form. There will be randomisation forms and lists for 12, 15 and 18 patients respectively and it is important to check if the correct form was used. For each patient the questions on informed consent, and inclusion/exclusion criteria on the form will be answered and the BBS Score will be entered. The fully completed form will then be faxed to the central randomisation office (Clinical Trials Unit, CTU) for randomisation:

**Clinical Trials Unit**

**Medical Center – University of Freiburg**

**[contact]**

The CTU will review the patient's details on the randomisation fax and randomise the patients. The result of the randomisation will be send to the investigator.

The treatment can be initiated for each patient group according to the randomised treatment arm. If the details on the randomisation fax appear incomplete or implausible, the CTU will send the investigator a query fax for clarification.

## 6 Study Procedures

### 6.1 Visit schedule and assessments - Flowchart

Table 1 Visit schedule and assessments – Flowchart of the Trial

VISITS	Pre-Treatment (Screening, Waiting time, Baseline/Visit 1 Randomisation)			Treatment					Post-Treatment Follow-up	
					Phone Visit 2-3 (b)	Visit 4 (c)	Phone Visit 5-6	Visit 7 (c)	Phone Visit 8-12 (b)	Last Visit, EOT (d)
TIME		Week -4 to Day -1		Day 0	Month 1 & 2	Month 3	Month 4 & 5	Month 6	Month 7- 11	Month 12
Pre-Screening	X									
Waiting time		X								
Randomization (a)			X							
Informed consent			X							
In-, exclusion criteria			X							
Demographic Data			X							
Handing out Study Book				X						
Fall prevention information				X						
Recommendation to visit primary care doctor				X						
Start treatment or control per patient (e)				X						
Review fall diary					X	X	X	X	X	X
BBS			X			X		X		X
MoCA			X			X		X		X
IADL			X			X		X		X

VISITS	Pre-Treatment (Screening, Waiting time, Baseline/Visit 1 Randomisation)				Treatment					Post-Treatment Follow-up	
						Phone Visit 2-3 (b)	Visit 4 (c)	Phone Visit 5-6	Visit 7 (c)	Phone Visit 8-12 (b)	Last Visit, EOT (d)
Medications			X			X		X		X	
Patient reported: Baseline Questions			X								
Patient reported: Short FES-I			X			X		X		X	
Patient reported: GDS-15			X			X		X		X	
Patient reported: SF-12			X			X		X		X	
Patient reported: ICPH (only EYT and Tai Chi group)						X		X			
Patient reported: FIMA			X			X		X		X	
Safety; complications					X	X	X	X	X	X	
6 month questionnaire								X			

- (a) The randomisation fax should be prepared as close as possible to the treatment.
- (b) Phone visits can be conducted up to +10 days
- (c) Visit 4 and 7 (month 3 and 6) can be conducted within  $\pm 2$  weeks
- (d) Last visit (month 12) can be conducted  $\pm 4$  weeks
- (e) The treatment should start at the same day or one day after but not more than seven days after handing out the study book

## 6.2 Study procedures at Study Sites

See also ("Recruitment and Enrolment of Subjects in the Study, Randomisation", section 5.)

The investigator will

- inform the subject about the project and ask for written consent (see section 16.1). The original consent form will be filed with the patient's source documents, the second form stays with the patient.
- ensure that only patients who meet all the inclusion and none of the exclusion criteria and which have free time to join the group sessions are randomised into the trial.
- a copy of the consent form needs to be filed in the investigator site file.
- organize or supervise the organization of appropriate rooms for group session (together with therapists and teachers).
- inform/supervise informing the EYT therapists and Tai Chi teachers about 1) recruitment progress, 2) expectable and 3) actual start of group sessions, to ensure timely start of the intervention.
- in case, therapists or teachers are unable or decline to conduct group sessions, supervise their timely replacement with qualified therapists or teachers and their instruction, supported by manuals provided by the Coordinating Investigator.
- supervise assessment of BBS, MoCA and filling in questionnaires (see section 2)
- ensure timely handing out of study book and start group sessions (at the most 4 weeks after baseline assessment)..
- in case that the patient withdraws his/her consent, the referring physician will complete a special form and inform the Clinical Trials Unit, Medical Center – University of Freiburg, via [contact]. The following information is transmitted: date of withdrawal, information whether the patient has given consent that his data collected up to the date of withdrawal can be retained for further usage in the study. This document need to be stored into the investigator site file (after information via fax).
- Investigator or study personnel instruct the patients how to report falls in the diary.

### **6.3 Baseline Assessment:**

Sociodemographic data, history, diagnoses, risk factors including:

- Age, gender, highest completed level of education and training, height, weight, BMI.
- Falls within last 6 months, with/without injuries), use of walking aid.
- Trouble vision, trouble hearing, vertigo, trouble walking.
- Diagnosis, (cardiovascular, orthostatic dysregulation, pulmonal, diabetes, other internistic, osteoporosis, mental condition, sleep disorder, history of stroke,

Parkinson disease, multiple sclerosis, polyneuropathy, other neurological, chronic arthritis of knee or hip or feet, other musculoskeletal).

- Sport/physical activity
- Social activity (living alone, with family, friends; socializing/meeting with friends, relatives, neighbours; social support through family, friends, neighbours.

The document asking for diagnoses should be signed by the investigator to make sure that patients understood and filled it out correctly

BBS is assessed by a study personnel, as well as MoCA and IADL, supported by written instructions.

The questionnaires *Short Falls Efficacy Scale-International*, *GDS-15*, *SF-12*, *ICPH*, *FIMA* are filled in by the patients. Study personnel will support patients to fill in questionnaires, particularly the *FIMA*, and check them for completeness. Also family members/next of kin or health care professionals can support patients to fill in the questionnaires (see do's and don'ts at table).

The questionnaires should be completed in the same environment, quiet and respectful of the subject's privacy and prior to other investigations. Patient reported questionnaires are to be filled out by the patient him/herself. It is important that the investigator or other study personnel do not influence the patient in any way during the completion of the questionnaire (see do's and don'ts at table).

The following checklist contains some “do's” and “don'ts” when administering the questionnaires (except baseline questions).

DOs	DON'Ts
Do have the subject complete the questionnaire and make sure questionnaire are filled in completely	Do not discuss the subject's health, health data, or emotions with them before they fill out the questionnaire
Do be warm, friendly and helpful	Do not force or command subjects to fill out the questionnaire
Do request and encourage subjects to fill out the questionnaire	Do not accept an incomplete questionnaire without first encouraging the subject to fill out unanswered questions
Do tell the subject to answer a question based on what they think the question means	Do not interpret or explain a question
Do have the subjects fill out the	Do not allow the wife/husband or

DOs	DON'Ts
questionnaire by themselves	family members to help the subject complete the questionnaire
Do encourage subjects to complete all questions	Do not minimise the importance of the questionnaire
Do inform subjects that they will be asked to fill out another questionnaire at a later date (if applicable)	Do not change any question since this will affect the scoring

The questionnaire MoCA is filled in by the investigator/physician or qualified study personnel on the basis of an interview with the patient or, if needed, by a family member/next of kin.

Data obtained from assessments done by the investigator or study nurse, as well as data obtained from patient's fall diary and training diary will be filed with the patient's source documents and documented into the eCRF by designated personnel of the study site (e.g. investigator or study nurse). Patient-reported questionnaires will be stored at the patient's source documents and a duplicate sent to the Clinical Trials Unit in Freiburg.

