
ENDPOINTS
	
Primary efficacy endpoint:
 
 
• Fall (yes/no) within 6 months recorded in diary (i.e. “fallers”).
 
 
Key secondary endpoints:
 
 
• Number of falls recorded in diary.
 
• Number of injurious falls.
 
• Fear of falling (Short Falls Efficacy Scale-International, Short FES-I).
 
• Mobility and Balance (Berg Balance Scale, BBS).
 
• Cognition (Montreal Cognitive Assessment, MoCA).
 
• Depression (Geriatric Depression Scale, GDS-15).
 
• Health-related quality of life (SF-12).
 
• Self-maintaining and instrumental activities of daily living (IADL).
 
• Inner Correspondence/Peaceful Harmony with Practices (ICPH).
 
• Health Care Utilization: Physician contacts, medication, hospitalizations (FIMA).
 
• use of recommendation of fall prevention brochure.
 
 
Assessment of safety:
 
Complications.

TRIAL DESIGN
	
Multi-centre, randomised controlled trial (1:1:1), stratified by study site, with two active and one control parallel groups.

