### 2.3 Secondary endpoints

Risk of falling at 12 months will be defined as in 2.2 within 12 months.

Injurious falls (total number) are subdivided by “moderate” and “serious” [48]:

- 1) Moderate injurious falls are defined as those that resulted in sprains, bruises, scrapes, or joint injuries or if the individual needed medical care
- 2) Serious injurious falls are defined as those that resulted in a fracture, head injury, tendon rupture, or admission to a hospital (inpatient care), or that required stitches.

The BBS is a 14-item scale primarily assessing standing balance and sit-to-stand positions. Scores are based on a 5-point scale, rating from 0 to 4, based on performance quality and duration, or assistance needed. “0” indicates the lowest and “4” the highest level of function. The total score ranges from 0 to 56 points [50].

The MoCA is a brief cognitive screening tool for mild cognitive impairment and assesses several cognitive domains. The total sum score ranges from 0 to 30 and higher scores indicate higher functioning [51].

The Short FES-I is a 7-item questionnaire to measure fear of falling in elderly patients during different activities. It is to be filled out by the patient him/herself. Each item is rated on a four-point scale from 1 (not at all concerned) to 4 (very concerned). The total score ranges from 7 (no concern about falling) to 28 (severe concern about falling) [49].

The GDS-15 is a short, 15-item instrument, developed and validated for measurement of depressive symptoms among elderly people. It is to be filled out by the patient him/herself. Its items require a yes/no response. The total score ranges from 0 to 15. Sum scores 0-4 are considered normal, sum scores 12-15 indicate severe depression, in between as mildly depressed [52].

The SF-12 is a short-form generic measure of health status from the patient’s point of view. It is to be filled out by the patient him/herself. It contains 12 items on 8 health concepts. Results are expressed in terms of two meta-scores: Physical Component Summary and Mental Component Summary. Scores range from 0 to 100. Higher scores indicate better functioning. The mean score in a representative sample of the US population is 50 [53].

The IADL evaluates complex instrumental activities of daily living, on 8 items. The total score ranges from 0 to 8 in women, and from 0 to 5 in men [54].

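### Section 6.3 lets a relative stand in for the MoCA, which decides eligibility, and separately gives opposite rules on family help with the patient-reported questionnaires

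*Protocol*

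**What the plan says.** **MoCA.** Section 2.3 describes the instrument thus: "The MoCA is a brief cognitive screening tool for mild cognitive impairment and assesses several cognitive domains". The total runs from 0 to 30, with higher scores meaning better functioning. Section 4.2 excludes patients scoring 18 or less, and section 5.2 names the MoCA among the tests needed to check eligibility. The Synopsis lists it as a key secondary endpoint, and the flowchart in section 6.1 schedules it at baseline and months 3, 6 and 12.

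Section 6.3 names the assessor twice. Before the checklist it says: "BBS is assessed by a study personnel, as well as MoCA and IADL, supported by written instructions". After the checklist it says that the MoCA is filled in by the investigator or qualified staff "on the basis of an interview with the patient or, if needed, by a family member/next of kin".

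**Patient-reported questionnaires.** Section 6.3 lists the Short FES-I, GDS-15, SF-12, ICPH and FIMA as completed by patients, with support from study personnel. It then adds: "Also family members/next of kin or health care professionals can support patients to fill in the questionnaires", and points to the checklist. The next paragraph states: "Patient reported questionnaires are to be filled out by the patient him/herself". The DON'Ts column of the checklist tells staff not to allow the spouse or "family members to help the subject complete the questionnaire".

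**The concern.** The MoCA scores what the patient can do in the test. A relative can describe a patient's memory or daily functioning, but cannot produce that patient's test performance. If a relative fills in the form or answers for the patient, the number on the 0 to 30 scale is not a MoCA score in the sense of section 2.3.

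Two uses of the score are then exposed. At entry, such a value may wrongly admit or wrongly exclude a patient at the 18-point threshold. As an endpoint, it gives an unsound baseline, and any change from it compares two modes of assessment.

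The questionnaire rules raise a different problem. A site that follows one sentence breaks the other, so sites may collect the same patient-reported outcomes under different conditions, with no record of which condition applied. Five of the eleven key secondary endpoints listed in the Synopsis rest on these instruments: fear of falling, depression, quality of life, ICPH and health-care utilization.

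**Working it through.** No arithmetic applies. The protocol gives no figure for how often a relative would be used, so the check is a comparison of the text.

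**A. Who obtains the MoCA**

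| Place | Assessor |
|---|---|
| 6.2 | Investigator supervises the assessment |
| 6.3, before the checklist | Study personnel, with written instructions |
| 6.3, after the checklist | Investigator or qualified staff, with a relative as fallback |
| 6.4 (follow-up) | Investigator, study nurse or patient; no relative named |

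1. The fallback clause has two possible meanings: the relative completes the form, or the relative is the person interviewed. On both, the score no longer comes from the patient's own performance.
2. The condition for the fallback is not defined. One natural case is a patient who has difficulty with the test, which is where the exclusion threshold has to work, but the protocol does not say so.
3. Sections 4.2 and 5.2 make the score an entry condition. Section 4 explains that major cognitive impairment excludes patients who could not take part in or benefit from group classes. A score from a relative does not serve that purpose.
4. The clause stands in the baseline section, and sections 5.2 and 5.3 place randomisation after baseline assessment. Use of a relative at that point cannot depend on the allocated arm.
5. For follow-up, section 6.4 gives no rule specific to the MoCA and refers to section 2, which does not say who administers it. A site might carry the section 6.3 sentence forward, but the text does not say so.

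**B. Family help with questionnaires**

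1. The permission directly follows the list of the five patient-completed instruments, so it covers them.
2. The checklist exempts only the baseline questions, so its ban covers the same five instruments.
3. The permission and the ban therefore apply to the same instruments and cannot both be followed. The self-completion sentence sides with the ban.
4. The permission also names health care professionals. The DON'Ts column bars only the spouse and family members, so on professionals the two places do not conflict.

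**C. Relation between A and B.** The permission concerns forms that the patient fills in. The MoCA is assigned to staff. The two defects share a section but are independent of each other.

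**The case against.** The case on the other side is substantial. Study personnel are the default assessors, the investigator supervises, and the relative is only a fallback. The MoCA is not the only safeguard at entry: final screening is done by the investigator in person, and section 4.2 separately excludes patients with sensory or language problems that affect understanding and patients without legal capacity who cannot understand the study. The MoCA plays no part in the sample size calculation, the multiplicity procedure or the primary model. On the questionnaires, the permission itself points to the checklist, and with the self-completion sentence beside it the intended rule can be guessed.

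All of this limits the size of the problem. It does not remove the contradictions: the fallback is written into the protocol, and staff should not have to guess which sentence governs.

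Three stronger readings are tempting, and the documents do not support them:

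- **That the MoCA as a whole is invalid in this trial.** Only scores obtained through a relative are unsound.
- **That relatives, knowing the allocation in an open-label trial, could selectively replace low follow-up scores and bias the comparison between arms.** Section 6.4 names no relative at follow-up, and baseline scores precede randomisation. Follow-up use is a possible inference, not something the protocol states.
- **That the conflict over family help damages the MoCA.** It concerns the patient-reported questionnaires only.

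**Conclusion.** Both defects hold. Section 6.3 allows the MoCA to be obtained by or from a relative, contrary to its own assignment of the test to study personnel. This can misclassify patients at the exclusion threshold and leave an unsound baseline value for one of eleven key secondary endpoints. Separately, the section both permits and forbids family help with five patient-reported instruments.

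The size cannot be calculated: the documents give neither the share of scores that would come from relatives nor the error in them. The conclusion rests on the wording and on one premise, that the MoCA measures the patient's own cognition, as section 2.3 describes it. The primary endpoint is affected at most through misclassification at entry. The point should be fixed, but it is not an obstacle to the trial's main comparison.

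**What to change.** **MoCA.** Delete the relative from the MoCA sentence in section 6.3. State that trained study personnel administer the MoCA to the patient at baseline and at months 3, 6 and 12, and repeat or cross-refer to this in section 6.4. Base eligibility only on a score obtained from the patient. Record a follow-up MoCA that cannot be done as missing, with the reason. At screening a missing value is not an adequate outcome, because the exclusion criterion could not be checked; the text should make this explicit.

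**Questionnaires.** Remove family members and next of kin from the permission in section 6.3 so that it agrees with the checklist. Do not delete the whole sentence, because it also covers health care professionals, whom the checklist does not bar. State instead what support by staff or professionals is allowed, and flag every assisted completion in the eCRF.

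**Cost.** About two sentences in section 6.3, matching site instructions and one eCRF field. A few follow-up MoCA values may be missing. Some patient-reported forms may be less complete without family help; the FIMA is the likeliest, since section 6.3 singles it out for staff support.
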